12.0 Descriptive Factors

- Breast: left vs. right
- AJCC Stage: 0 vs IA vs IB vs IIA vs IIB vs IIIA
- Tumor Size: 0-2cm vs > 2-5cm vs > 5cm
- Lymph Nodes: N0 vs N1

13.0 Treatment/Follow-up Decision at Evaluation of Patient

Follow-up data will be collected and entered after the observation phase outlined in section 4.0. If the patient is still alive after 5 years have elapsed from the on-study date, no further follow-up is required by this protocol.

- 13.1 Patients who have a recurrence while receiving therapy or during observation will go to the event-monitoring phase and be followed
- 13.2 Patients who discontinue treatment or observation for reasons other than recurrence will go to the event-monitoring phase and be followed
- 13.3 Patients who will not receive any radiation treatment or who will receive radiation treatment elsewhere will move to event monitoring phase.
- 13.4 A patient is deemed *ineligible* if after registration, it is determined that at the time of registration, the patient did not satisfy each and every eligibility criteria for study entry. The patient may continue treatment off-protocol at the discretion of the physician as long as there are no safety concerns, and the patient was properly registered. The patient will go directly to the event-monitoring phase of the study (or off study, if applicable).

If the patient received treatment, all data up until the point of confirmation of ineligibility must be submitted. Event monitoring will be required per Section 18.0 of the protocol.

If the patient never received treatment, on-study material and the End of Active Treatment/Cancel Notification Form must be submitted. No further data submission is necessary.

- 13.5 A patient is deemed *withdrawn* if she is removed from the study for any reason before any study treatment is given. On-study material and the End of Active Treatment/Cancel Notification Form must be submitted. No further data submission is necessary.

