16.0 Statistical Considerations and Methodology

- 16.1 Overview: This is an open label phase III randomized controlled trial to determine the safety of 5 fraction vs 15 fraction radiotherapy after breast conserving surgery. The goal is to determine whether the difference in 24-month complication rates between the experimental arm and the control arm is acceptable. Of interest is whether the experimental arm results in an unacceptable increase in the 24-month complication rate. If it does not, then the experimental arm will be recommended for further study. If the 24-month complication rate is found to be unacceptable, then the recommendation would be to do no further studies of the experimental arm.

- 16.2 Primary and Secondary Endpoints

16.21 Primary Endpoint: The 24-month complication rate, defined as the percentage of women evaluable at 24 months who develop one or more of the following events:

- 1) grade 3 or higher late adverse event OR
- 2) deterioration of cosmesis from excellent/good to fair/poor or from fair to poor at the 24-month evaluation (using the Harvard/NSABP/RTOG Cosmesis Scale)

16.22 Secondary Endpoints:

16.221 Acute and late adverse events including grade ≥ 2 pneumonitis.

16.223 Locoregional control, invasive disease-free, distant recurrence, disease-free survival, cause-specific survival, overall survival.

The following definitions are used for the secondary endpoints of interest:

- *Acute adverse events*: any adverse event, regardless of attribution, that occurs in the first 90 days post-RT.
- *Late adverse events* (up to 5 years post RT): any adverse event that occurred after the first 90 days post-RT and up to 5 years post-RT.
- *Ipsilateral breast tumor recurrence (IBTR)*: this is defined as local recurrence from trial registration as a first event at 5 years. IBTR is defined as both invasive and non-invasive breast cancer involving the same breast parenchyma as the original tumor.
- *Regional recurrence*: invasive breast cancer in the axilla, regional lymph nodes, chest wall, and skin of the ipsilateral breast at 5 years.
- *Distant recurrence*: metastatic cancer that has either been biopsy confirmed or clinically diagnosed as recurrent invasive breast cancer at 5 years.

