16.6 Analysis Plan

The analysis for this trial will commence at the planned time points and at the time the patients have become evaluable for the primary endpoint.

16.6.1 Primary Analysis: The primary analysis will be to estimate the difference in the complication rate (adverse cosmesis and grade 3+ toxicities) which is defined as the 24-month complication rate in experimental arm minus that in the control arm. All patients meeting the eligibility criteria who have signed a consent form and started treatment will be in the primary analysis. The complication rate will include all women evaluable at 24 months. Those who have recurrent disease or die before 24 months will not be included in this calculation. We expect that <3% of patients will not be found eligible based on failure or death.²⁴ The complication rate will be estimated using a binomial estimator in both experimental arm

and control arm, and a one-sided 90% confidence interval of the difference will be computed with normal approximation. As mentioned above, the following decisions will be made based on the 90% CI:

- ***The upper bound of the 1-sided 90% CI of the difference lies below 15%:*** The experimental arm regimen is acceptable.
- ***The upper bound of the 1-sided 90% CI of the difference lies above 15%:*** The experimental arm regimen is unacceptable.

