18.0 Records and Data Collection Procedures

18.1 Submission Timetable

Initial Material(s) -

CRF	Treatment (Compliance with Test Schedule Section 4.0)
Institutional Contacts	
Patient Eligibility	
Demographics	
On-Study	≤2 weeks after registration
On Study: Neoadjuvant Chemotherapy	
Surgery	
Pathology of Ipsilateral Breast	
Adjuvant Therapy	
Adverse Events- Baseline	
Patient Status: Baseline	
Patient Assessment	*6 months after accrual
Off Treatment	Submit ≤2 weeks after registration if withdrawal/refusal occurs prior to beginning protocol therapy

Test Schedule Material(s)

CRF	End of Treatment	12 weeks post/Observation Phase ⁴	Event Monitoring ⁵
Radiation Therapy	X		
Radiation Lumpectomy Therapy	X		
Patient Assessment	X	X	
Adverse Events Solicited	X	X	
Adverse Events: Other	X ²	X ²	
Off Treatment	X ²	X ²	
Patient Status Form	X	X	X

CRF			
	End of Treatment	12 weeks post/Observation Phase ⁴	Event Monitoring ⁵
Specimen Submission: Pathology Report (Recurrence)		X ²	
Consent Withdrawal	X ²	X ²	
Lost to Follow-up	X ²	X ²	
Breast Radiotherapy Questionnaire ³	X	X	

1. Complete at each evaluation during Active Treatment (see Section 4.0).
2. When applicable
3. Survey will need to be entered manually if has not alternately been scanned or entered electronically
4. **Refer to test schedule in section 4.0** If patient has a recurrence prior to being off radiation therapy for 5 years, continue to follow yearly.

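### Women moved to event monitoring before 24 months have no scheduled cosmesis score or solicited late adverse event form, and the primary analysis has no rule for them

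*Combined protocol and SAP*

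**What the plan says.** Section 13.2 of the combined protocol and SAP sets the route: "Patients who discontinue treatment or observation for reasons other than recurrence will go to the event-monitoring phase and be followed".

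Section 18.1 sets what is collected on that route. As the table can be read, "Patient Status Form" is the only row marked under event monitoring. "Adverse Events Solicited", the form for other adverse events, the patient assessment and the breast questionnaire are marked for end of treatment and for the observation phase, not for event monitoring. The event-monitoring column refers to a footnote 5 whose text is not in the material available. No row names the nurse-scored cosmesis scale; I assume that it sits on the patient assessment form.

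Section 16.6.1 defines the population: "All patients meeting the eligibility criteria who have signed a consent form and started treatment will be in the primary analysis". It then narrows the calculation: "The complication rate will include all women evaluable at 24 months". Only recurrence and death are named as grounds for leaving a woman out. Section 16.21 places the cosmesis component at one visit: "deterioration of cosmesis from excellent/good to fair/poor or from fair to poor at the 24-month evaluation". Section 16.22 defines a late adverse event as "any adverse event that occurred after the first 90 days post-RT and up to 5 years post-RT".

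**The concern.** Read together, these sections leave a gap. A woman who receives some radiotherapy, stops for a cause other than recurrence and is moved before 24 months belongs to the primary population. Yet no visit is scheduled at which her cosmesis could be scored, and no solicited late adverse event form is due. Evaluability is not defined, and there is no imputation rule or sensitivity analysis for her. On the natural reading she disappears from both numerator and denominator.

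The 10 extra women in Section 16.4 protect power against such losses, but they do not protect against bias. If loss is related to outcome and differs between arms, the estimated difference shifts, and with about 50 women per arm a small shift can decide the trial.

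**Working it through.** **1. The plan's own figure.** Inputs from Sections 16.4 and 16.5: 50 evaluable per arm, 10% in both arms, margin 15 points, one-sided alpha 0.05. SE = √(2 × 0.10 × 0.90 / 50) = 0.060. Power = Φ(0.15/0.060 − 1.645) = Φ(0.855) = 80.4%, which reproduces the stated 80%. With the one-sided 90% bound written in Section 16.6.1, power is Φ(2.5 − 1.282) = 88.8%. Both bounds are carried below because the plan uses both; that mismatch is a separate matter.

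**2. Loss unrelated to outcome.** Losing 5 of 55 per arm leaves 50 and 80.4% power (95% bound). Losing 8 per arm leaves 47 and 78.2%. Random loss matters little.

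**3. Informative loss from the 5-fraction arm only.** The documents give neither a discontinuation rate nor the complication risk of women who discontinue, so these are assumptions: 55 women in the 5-fraction arm, true rates 25% and 10% (the null in Section 16.5), 50 control women evaluable, d women lost, and a fraction q of those with complications.

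- Observed rate: p = (0.25 × 55 − q·d) / (55 − d)
- SE = √(0.10 × 0.90/50 + p(1 − p)/(55 − d))
- Chance of false acceptance = Φ((0.15 − (p − 0.10))/SE − z), with z = 1.645 or 1.282

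For d = 2:
- q = 50%: p = 12.75/53 = 24.06%, difference 14.06 points, SE 0.0724; result 6.5% (z = 1.645) or 12.5% (z = 1.282).
- q = 100%: p = 11.75/53 = 22.17%, difference 12.17 points, SE 0.0711; result 10.6% or 18.8%.

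| Women lost (5-fraction arm) | 95% bound, q = 50% to 100% | 90% bound, q = 50% to 100% |
|---|---|---|
| any number, q = 25% | 5.0% | 10.0% |
| 1 | 5.7% to 7.3% | 11.2% to 13.8% |
| 2 | 6.5% to 10.6% | 12.5% to 18.8% |
| 3 | 7.4% to 15.1% | 13.9% to 25.2% |
| 5 | 9.7% to 29.1% | 17.4% to 42.6% |

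Exact enumeration for two women lost gives 7.0% to 11.3% (95% bound) and 13.0% to 19.4% (90% bound), against 5.4% and 10.4% with uninformative loss. The normal approximation is adequate here. The row for five women is an outer limit: it spends the arm's whole allowance on this one route.

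**4. The same loss in both arms.** If each arm loses d women with the same q, the observed difference is (13.75 − 5.5)/(55 − d) = 8.25/(55 − d), whatever q is. That is 15.6 points for d = 2 and 16.5 for d = 5. It does not shrink.

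**5. Loss from the control arm only.** With d = 2, the control rate falls to 4.5/53 = 8.5% (q = 50%) or 3.5/53 = 6.6% (q = 100%). The observed difference grows to 16.5 or 18.4 points, which works against the 5-fraction arm.

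**6. Fragility of the decision.** With 5/50 control events, 7/50 in the 5-fraction arm passes at the 95% bound (upper bound 14.7%). Restoring one unobserved complication (8/51) gives 16.6% and reverses the decision. At the 90% bound, 8/50 passes (14.6%) and 9/51 fails (16.4%).

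**The case against.** The strongest reply has five parts.

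- **Data are not wholly lost.** Adverse events up to the move are on file, and Section 10.5 asks for grade 3 to 5 events outside the Section 10.4 list with no limit on study phase. This stands, but it covers little of the endpoint. Section 16.4 expects late grade 3+ toxicity in at most 1%, against an assumed 10% complication rate, so cosmesis carries nearly all of it. Fibrosis, breast edema and radiation dermatitis are Section 10.4 items and so fall outside Section 10.5.
- **Women who stop need not be those with complications.** A reader might infer that they are the likeliest to have one. The documents do not support this. Section 13.2 covers every non-recurrence reason. A 5-day or 3-week course ends well before the 90-day threshold for late events, so stopping during it would mostly reflect acute effects, which the endpoint does not count.
- **The direction is open.** A reader might infer that the gap favours non-inferiority. Steps 4 and 5 show that this needs loss concentrated in the 5-fraction arm. If stopping follows course length, the longer control arm could lose more. This stands.
- **The table is machine-read.** The missing footnote might add forms to event monitoring. This stands as a caveat, and the sponsor can settle it quickly.
- **Women who have left observation cannot be ordered back.** Note 12 in Section 4.0 already provides for seeking outside records. This stands, and limits what an amendment can recover. But note 12 accepts that required items may be missing, and note 13 waives the cosmetic assessment at outside visits, so neither supplies the missing score.

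**Conclusion.** The gap in data collection is real, subject to confirmation of footnote 5, and no other section closes it. A woman moved before 24 months is counted into the primary population but has no scheduled means of contributing the main component of the endpoint.

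The statistical consequence is conditional. Bias requires loss that is both informative and different between arms. In an open-label comparison of 5 with 15 fractions that cannot be excluded, but neither its presence nor its direction can be read from the documents. Under the stated assumptions, two women lost from the 5-fraction arm alone raise false acceptance from 5% to about 6.5–11% (95% bound) or from 10% to about 12.5–19% (90% bound). The numbers lost and their complication risk are assumptions.

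Two further readings should be avoided. These women do not supply nothing: what is missing is scheduled cosmesis and solicited adverse event data after the move. Nor does each lost woman shift the rate by 2 points. She leaves numerator and denominator together, so two lost complications move 25.0% to 22.2%, about 1.4 points each. The point merits correction because data not collected by 24 months cannot be recovered at analysis.

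**What to change.** 1. Amend Section 13.2 so that women who received any protocol radiotherapy and stop treatment without recurrence stay on the Section 4.0 adverse event and cosmesis assessments through 24 months, unless they withdraw consent or decline visits, and only then enter event monitoring. This concerns outcome collection only; it does not alter when or why treatment is stopped.
2. Mark the Section 18.1 forms to match, and supply or confirm the text of footnote 5.
3. In Section 16.6.1, define who is evaluable, and count a late adverse event of grade 3 or higher recorded before a woman leaves as an event whatever follows.
4. Report missing 24-month cosmesis by arm and reason, with a tipping-point analysis showing how many unobserved complications in each arm would reverse the decision. This also covers women who decline further visits, whom item 1 cannot reach.

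The cost is a few extra visits, a minor amendment and one added sensitivity table.

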14.0 Body Fluid Bio-specimens

- 14.1 N/A

15.0 Drug Information

Not Applicable

16.0 Statistical Considerations and Methodology

- 16.1 Overview: This is an open label phase III randomized controlled trial to determine the safety of 5 fraction vs 15 fraction radiotherapy after breast conserving surgery. The goal is to determine whether the difference in 24-month complication rates between the experimental arm and the control arm is acceptable. Of interest is whether the experimental arm results in an unacceptable increase in the 24-month complication rate. If it does not, then the experimental arm will be recommended for further study. If the 24-month complication rate is found to be unacceptable, then the recommendation would be to do no further studies of the experimental arm.

- 16.2 Primary and Secondary Endpoints

16.21 Primary Endpoint: The 24-month complication rate, defined as the percentage of women evaluable at 24 months who develop one or more of the following events:

- 1) grade 3 or higher late adverse event OR
- 2) deterioration of cosmesis from excellent/good to fair/poor or from fair to poor at the 24-month evaluation (using the Harvard/NSABP/RTOG Cosmesis Scale)

16.22 Secondary Endpoints:

16.221 Acute and late adverse events including grade ≥ 2 pneumonitis.

16.223 Locoregional control, invasive disease-free, distant recurrence, disease-free survival, cause-specific survival, overall survival.

The following definitions are used for the secondary endpoints of interest:

- *Acute adverse events*: any adverse event, regardless of attribution, that occurs in the first 90 days post-RT.
- *Late adverse events* (up to 5 years post RT): any adverse event that occurred after the first 90 days post-RT and up to 5 years post-RT.
- *Ipsilateral breast tumor recurrence (IBTR)*: this is defined as local recurrence from trial registration as a first event at 5 years. IBTR is defined as both invasive and non-invasive breast cancer involving the same breast parenchyma as the original tumor.
- *Regional recurrence*: invasive breast cancer in the axilla, regional lymph nodes, chest wall, and skin of the ipsilateral breast at 5 years.
- *Distant recurrence*: metastatic cancer that has either been biopsy confirmed or clinically diagnosed as recurrent invasive breast cancer at 5 years.
- *Invasive disease-free survival*: this is defined as the time from study registration until the occurrence of one of the events in a composite endpoint. This endpoint includes invasive IBTR, regional invasive breast cancer recurrence, distant breast cancer recurrence, death due to any cause.
- *Disease-free survival*: this is defined as the time from study registration until the occurrence of one of the events in a composite endpoint. This endpoint includes any IBTR, regional invasive breast cancer recurrence, distant breast cancer recurrence, death due to any cause,
- *Cause specific survival*: is defined as the time from registration to death due to breast cancer. If the cause of death is unknown or difficult to establish patients with a distant failure at the time of death would be censored as dying from breast cancer
- *Overall survival*: is defined as the time from registration to death due to any cause.

16.3 Exploratory endpoints:

16.31 Patient self-reported cosmesis evaluate fatigue, breast pain, arm function and other patient reported outcomes.

The following definitions are used for the exploratory endpoints of interest:

- *Patient Reported Outcomes/Quality of life:* Elements of the Patient-Reported Outcomes Version of the Common Terminology Criteria for Adverse Events (PRO-CTCAE) will be used for patient self-reporting of toxicities. The Breast Cancer Treatment Outcomes Scale (BCTOS) will be used to measure patient reported functional status (pain, mobility). Other measures of fatigue, pain, and arm function are listed in the appendix.
- *Patient self-reported cosmetic outcomes:* the patient self-reported outcome will be assessed using a modified Harvard Cosmesis Scale and the BCTOS at baseline, 2 years, and 5 years.
- *Panel assessed cosmetic outcome:* in addition to patient self-reported and physician reported outcomes, cosmesis will be assessed by a panel of breast cancer medical providers using digital photographs from baseline and at 2 years. The Panel will be blinded to treatment allocation.

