5.0 Stratification Factors

- 5.1 Treatment modality: Photons vs. spot scanned proton therapy. Of the total 110 patients in this study, fifty-five would be treated in each arm. We will

allow a maximum of 28 patients per arm per treatment modality (photons/x-ray or protons).

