16.62 Secondary Analyses

16.621 *Acute adverse events:* All patients who were registered to the study and started treatment will be included in the acute adverse event analysis. An acute adverse event is an AE, regardless of attribution, that occurs up to 90 days post-RT. The maximum grade for each type of acute AE will be recorded for each patient. Data will be summarized as frequencies and relative frequencies by treatment arm. Additionally, the relationship of the adverse event(s) to the study treatment will be taken into consideration. Rates will be compared between arms using chi-squared tests.

16.622 *Late adverse events:* All patients who were registered to the study and started treatment will be included in the late adverse event analysis. A late adverse event is an AE, regardless of attribution, that appears or persists after 90 days post-RT and up to 5 years post-RT. The maximum grade for each type of late AE will be recorded for each patient. Data will be summarized as frequencies and relative frequencies by treatment arm. Additionally, the relationship of the adverse event(s) to the study treatment will be taken into consideration. Rates will be compared between arms using chi-squared tests.

16.623 *Locoregional control:* The cumulative incidence of locoregional recurrence will be estimated using a competing risks method (Gooley et al.) by treatment arm. The competing risks will be distant breast cancer recurrence and death. Comparison between arms will employ Fine-Gray regression.

16.624 *Invasive disease-free survival:* i-DFS is defined as the time from registration until the time of invasive disease recurrence (not including DCIS) or death due to any cause. The i-DFS will be estimated with a Kaplan-Meier estimator and curve by treatment arm. Estimates will be given for specific time points along with 95% CIs. Comparison between arms will employ a log-rank test.

16.625 *Disease-free survival:* DFS is defined as the time from registration until the time of disease recurrence or death due to any cause. The DFS will be estimated with a Kaplan-Meier estimator and curve by treatment arm. Estimates will be given for specific time points along with 95% CIs. Comparison between arms will employ a log-rank test.

16.626 *Cause specific survival:* The CSS will be estimated with a Kaplan-Meier estimator and curve by treatment arm. Estimates will be given for specific time

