points along with 95% CIs. Comparison between arms will employ a log-rank test.

16.627 *Overall survival:* The OS will be estimated with a Kaplan-Meier estimator and curve by treatment arm. Estimates will be given for specific time points along with 95% CIs. Comparison between arms will employ a log-rank test.

16.631 *Quality of life:* The subscales of the BCTOS, elements from CTCAE-PRO, and other patient reported measures such as fatigue, breast pain, breast shape, and arm related morbidity outlined in the appendix will be summarized as the mean \pm SD and median (minimum value, maximum value). Mixed models will be used to estimate changes at fixed time points as well as compare outcomes between arms.

16.632 *Cosmesis:* The values of the cosmesis instruments (patient self-reported and panel-assessed) will be summarized with the frequencies and confidence intervals of fair or poor cosmesis events at baseline, 2 years, and 5 years by treatment arm. Comparisons between arms will employ chi-squared tests.

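### The cause-specific survival rule for deaths of unclear cause contradicts itself: it tells the analyst to code the same death as censored and as a breast cancer death

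*Combined protocol and SAP*

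**What the plan says.** Section 16.22 of the combined protocol and SAP states that cause-specific survival "is defined as the time from registration to death due to breast cancer". For deaths whose cause is not known or is hard to determine, it adds that "patients with a distant failure at the time of death would be censored as dying from breast cancer".

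Section 16.626 names the analysis: "The CSS will be estimated with a Kaplan-Meier estimator and curve by treatment arm". Estimates at chosen time points come with 95% confidence intervals, and "Comparison between arms will employ a log-rank test".

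The documents do not say how the CSS analysis treats deaths of known other cause, or deaths of unknown cause in women without distant failure. I find no other instruction on censoring.

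For arm size and duration, section 5.0 says "fifty-five would be treated in each arm", and section 13.0 says "If the patient is still alive after 5 years have elapsed from the on-study date, no further follow-up is required by this protocol".

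**The concern.** Kaplan-Meier and the log-rank test need one status code per patient: event or censored. The rule assigns both to the same death. It stands in the statistical section, where censoring is a technical term, so a programmer could reasonably take it at its word. The women concerned had distant failure when they died and are the most likely of those with unclear cause to have died of breast cancer. Coding them as censored therefore errs in one direction: CSS in that arm is too high.

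The situation can be foreseen. Under section 13.1, women with recurrence move to event monitoring, for which the table in 18.1 marks only the Patient Status Form. Note 12 to the schedule in section 4.0 accepts that follow-up may rely on outside records and that some required items may be missed. The trial is open label, so the coding should be settled before outcomes by arm are known. CSS is a listed secondary endpoint (16.223), and 16.8 commits to public reporting of secondary endpoints.

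**Working it through.** The plan gives no event count, rate or power for CSS, so there is no figure of its own to reproduce. The check below sizes the ambiguity, and then the separate question of the estimator.

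**Inputs from the documents.** n = 55 per arm (section 5.0); 5 years of follow-up (section 13.0); Kaplan-Meier (16.626).

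**Assumptions.** The numbers of deaths are illustrative. All other women in the arm are followed alive to 5 years.

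**Step 1: effect of the coding.** Let d be the number of breast cancer deaths in an arm, of which u have unclear cause with distant failure.

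- Coded as events: CSS = (n − d)/n.
- Coded as censored, all before the other deaths: CSS = (n − d)/(n − u).
- Coded as censored, all after the other deaths: CSS = (n − d + u)/n.

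| d | u | Coded as events | Coded as censored | Difference (points) |
|---|---|---|---|---|
| 1 | 1 | 54/55 = 98.18% | 100% | 1.82 |
| 3 | 1 | 52/55 = 94.55% | 52/54 = 96.30% to 53/55 = 96.36% | 1.75 to 1.82 |
| 3 | 2 | 52/55 = 94.55% | 52/53 = 98.11% to 54/55 = 98.18% | 3.57 to 3.64 |

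Each affected woman is worth about 1/55 = 1.8 points of 5-year CSS in her arm.

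**Step 2: does the choice of Kaplan-Meier add a material error?** Suppose deaths of other cause are censored. With constant hazards, let c1 and c2 be the 5-year cumulative incidences of breast cancer death and other death. The total cumulative hazard is L = −ln(1 − c1 − c2), the breast cancer part is L × c1/(c1 + c2), and 1 − KM = 1 − exp(−L × c1/(c1 + c2)).

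- c1 = c2 = 1%: 1 − KM = 1.01%, a difference of 0.01 points from c1.
- c1 = c2 = 5%: L = 0.1054, half is 0.0527, 1 − KM = 5.13%, a difference of 0.13 points.
- c1 = c2 = 10%: L = 0.2231, half is 0.1116, 1 − KM = 10.56%, a difference of 0.56 points.

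Over assumed risks of 1% to 10% for each cause, the gap runs from 0.01 to 0.56 points. One miscoded death outweighs it throughout that range.

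**The case against.** The strongest reply is that the sentence has a natural meaning. The endpoint is death from breast cancer, and the rule picks out women with distant failure and labels them as dying from that disease. The label would serve no purpose if they were to be dropped as non-events. The word censored most likely stands for coded, and on that reading the estimate is the intended one. This stands. A reader might infer that the planned CSS estimate is wrong, but the documents support only that the rule is ambiguous and that one reading gives a biased result.

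A reader might also infer that Kaplan-Meier is itself an error, or that it conflicts with 16.623, where "The cumulative incidence of locoregional recurrence will be estimated using a competing risks method". Neither follows. Censoring deaths of other cause is a conventional way to estimate CSS, and the log-rank test then compares cause-specific hazards. In 16.623, "The competing risks will be distant breast cancer recurrence and death", with death not limited by cause. For CSS, breast cancer death is the event and only death from other causes competes. The competing events differ, so the plan does not treat one competing event in two ways.

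Finally, a reader might infer that the ambiguity could change the comparison between arms. The documents cannot show this. The only related figure is in 16.4, a 2-year local failure and death rate below 3% in a cited trial. An affected woman must have distant failure, die within 5 years and have an unclear cause of death. How many such women there will be, and in which arm, is not given.

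**Conclusion.** The rule contradicts itself and should be corrected. Read literally, it biases 5-year CSS upward by about 1.8 points per affected woman in her arm. That size assumes 55 women analysed per arm and otherwise complete follow-up. The total effect is unknown because the documents give no expected number of these deaths, and it is zero if the phrase is applied as probably meant.

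The matter is minor. CSS has no power statement and is not named in the 5-year objective in 2.22. The recommendation in 16.5 and 16.6.1 rests on the 24-month complication rate alone. The Kaplan-Meier and log-rank choice needs no correction.

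**What to change.** 1. In 16.22, replace the contradictory phrase so that women with distant failure and an unknown or unclear cause of death *will be counted as deaths from breast cancer (events)*.
2. In 16.626, state that deaths of known other cause are censored at the date of death. The Kaplan-Meier choice implies this, but it is not written.
3. In the same edit, say how deaths of unknown cause without distant failure are coded, since the present rule leaves them out.

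Keep Kaplan-Meier and the log-rank test. If the team wishes, add the cumulative incidence of breast cancer death, with death from other causes as the competing risk, as a supplement; 16.623 already plans a method of that kind. The cost is a few lines of text, with no change to conduct, data collection or sample size. The change should be made before outcomes by arm are examined.
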